15 OTHER INFORMATION

15.1 Publication and Disclosure Policy

Publication and disclosure policy is addressed in a separate agreement.

15.2 Termination of the Study

If the study is terminated prematurely or suspended, the appropriate IRB will be promptly informed of the termination or suspension and will be provided the reason(s) for the termination or suspension. All obligations and responsibilities of the Sponsor and the Investigator will remain in force if the study is terminated prematurely.

Appendix A: Study Schedule of Events

Appendix B: Select Study Questionnaires

Appendix C: Signature Page

APPENDIX A: STUDY SCHEDULE OF EVENTS

Study Encounter (physical or virtual)	Baseline E1	E2	End of Study E3	Early Termination Visit
Week [†]		Wk 8 (± 7 d)	Wk 24 (± 14 d)	-
Informed consent	X			
Selection criteria	X			
Demographics & baseline clinical characteristics ¹	X			
Physical examination ²	X	X		
AK medical history and relevant comorbidites ³	X	X		X*
Tirbanibulin dose ⁴	X			
Prior AK medication (since diagnosis & past 6 months)	X			
Concomitant general medication	X	X		X*
Concomitant anti-AK medication	X	X	X	X*
Site Investigator assessments ⁵	X	X	X	X*
Study subject questionnaires ⁶	X	X	X	X*
AEs/SAEs ⁷	X	X	X	X*
Reasons for premature study withdrawal				X

*Collected, if relevant.

† Expected in-person or virtual encounter schedule, in relation to the index date (date of first administration of tirbanibulin).

¹ Clinical characteristics data assessed retrospectively based on what is documented in patient medical charts.

² Routine physical examination conducted as part of usual care alone and as documented in patient medical charts; such data may include - blood pressure, waist circumference, height/weight measurements.

³ May include AK date of diagnosis, baseline severity, relevant comorbidities, per clinician judgment and/or as documented in patient medical charts immediately before the index date; new emerging comorbidities during the study period will be recorded, based on the documentation in patient medical charts.

⁴ Expected usage is once daily, every day during the duration of the trial.

⁵ Site Investigator assessments may be conducted during subject visit to clinician offices, or via remote/virtual (telehealth) visits owing to Covid-related travel restrictions; this will include data related to LSRs.

⁶ Subject self-assessments may include assessment of AK, HRQoL, treatment satisfaction, and future preferences; Subjects will enter data into online portal or study mobile App.

⁷All AE information will be reported in the eDCF. If the SAE/Serious ADR has not resolved or stabilized by the time the subject completed the final study encounter or at the time of Subject's termination from the study, the Site Investigator may subsequently follow-up with the Subject to check the status of Subject's SAE/Serious ADR, prior to completing the eDCF for Subject's last encounter, if feasible.

Note: AE, adverse event; eDCF, electronic Data Collection Form; V, visit; W, week.

APPENDIX B: SELECT STUDY QUESTIONNAIRES

Expert Panel Questionnaire (EPQ)

1. Compared to {8 or 24} weeks ago (at the beginning of the study), how has the **overall appearance of the skin** in the original AK treated area changed?
 Much worse
 Somewhat worse
 No change
 Somewhat improved
 Much improved
2. How satisfied are you with this treatment's **ability to improve how your skin looks** (example: reduced redness, discoloration, crusting, scaling) in the original {or most recent} AK treated area?
 Extremely Dissatisfied
 Very Dissatisfied
 Dissatisfied
 Somewhat Satisfied
 Satisfied
 Very Satisfied
 Extremely Satisfied
3. How satisfied are you with this treatment's **ability to improve your skin texture** (i.e., how your skin feels in terms of roughness, bumpiness, scaliness) as a result of the treatment, in the original {or most recent} AK treated area?
 Extremely Dissatisfied
 Very Dissatisfied
 Dissatisfied
 Somewhat Satisfied
 Satisfied
 Very Satisfied
 Extremely Satisfied
4. Compared to your previous experience with topical treatment X for AK, how would you rate the **duration of skin reactions** (i.e., how long the skin reactions lasted) associated with tirbanibulin (Klisyri®) in the original AK treated area?

- Duration of skin reactions was much shorter with tirbanibulin
- Duration of skin reactions was somewhat shorter with tirbanibulin
- Duration of skin reactions was the same with tirbanibulin
- Duration of skin reactions was somewhat longer with tirbanibulin
- Duration of skin reactions was much longer with tirbanibulin

5. Compared to your previous experience with topical treatment X for AK, how would you rate the **severity of skin reactions** (i.e., how bad the skin reactions were) associated with tirbanibulin

(Klisyri®) in the original AK treated area?

- Severity of skin reactions was much better with tirbanibulin
- Severity of skin reactions was somewhat better with tirbanibulin
- Severity of skin reactions was about the same with tirbanibulin
- Severity of skin reactions was somewhat worse with tirbanibulin
- Severity of skin reactions was much worse with tirbanibulin

6. Compared to your previous experience with treatment X, how would you rate the **impact on your**

daily activities (such as shopping, bathing, social engagements, scheduling vacations, outdoor

activities, activities at work, attendance at work, etc.) due to skin reactions associated with

tirbanibulin (Klisyri®) use in the original AK treated area?

- Much better with tirbanibulin
- Somewhat better with tirbanibulin
- Same with tirbanibulin
- Somewhat worse with tirbanibulin
- Much worse with tirbanibulin

7. Compared to your previous experience with topical treatment X for AK, how would you rate the

convenience / ease of use (such as frequency of use, easy to follow instructions, comfortable at

apply, etc.) associated with tirbanibulin (Klisyri®) treatment?

- Ease of use & convenience was much better with tirbanibulin
- Ease of use & convenience was somewhat better with tirbanibulin
- Ease of use & convenience was the same with tirbanibulin
- Ease of use & convenience was somewhat worse with tirbanibulin
- Ease of use & convenience was much worse with tirbanibulin

8. Compared to your previous experience with topical treatment X for AK, how would you rate your **overall satisfaction** (considering the factors such as convenience/ ease of use, duration and severity of skin reactions, impact on daily life, etc.) with tirbanibulin (Klisyri®) treatment?

- My satisfaction is much better with tirbanibulin
- My satisfaction is somewhat better with tirbanibulin
- My satisfaction is same with tirbanibulin
- My satisfaction is somewhat worse with tirbanibulin
- My satisfaction is much worse with tirbanibulin

9. In case you need to be retreated for AK, how likely are you to consider tirbanibulin (Klisyri®) again?

- Very unlikely
- Somewhat unlikely
- Neutral
- Somewhat likely
- Very likely

10. Overall, how is your patient's AK in the original treated area right now?

- Completely cleared** - Approximately 100% clearance of AK lesions in the treated area
- Partially cleared** - Approximately $\geq 75\%$ clearance of AK lesions in the treated area
- Moderately cleared** - Approximately 50-74% clearance of AK lesions in the treated area
- Minimally Cleared** - Approximately $<50\%$ clearance of AK lesions in the treated area
- Not Cleared** - Approximately 0% clearance, i.e., all AK lesions remained in the treated area

11. How do you rate the current severity of skin photodamage in the original AK treated area?

Note: Photodamage can be described as alterations in the structure, function, and appearance of the skin as a result of prolonged or repeated exposure to ultraviolet (UV) radiation from the sun or other UV sources.

- Absent** - Smooth evenly pigmented skin
- Mild** - Freckling and/or other dyspigmentation
- Moderate** - Above plus mildly rough "dry" skin, fine wrinkling and/or telangiectasias or blotchy erythema
- Severe** - Above plus pronounced "dryness" and/or dyspigmentation and/or telangiectasia or erythema, and/or wrinkling, with or without areas of actinic purpura

Note:

- For Subjects re-treated with another topical treatment (other than tirbanibulin) at Week-24, questions 3-8 are reworded to enable the assessment of relative satisfaction associated with tirbanibulin in comparison to the ‘most recent topical treatment for AK’.
- The clinician version of the questions 3-8 will refer to clinician experience / observation of tirbanibulin effects among their patients.
- Questions 10 & 11 are answered only by clinicians.

TSQM-9

Abbreviated Treatment Satisfaction Questionnaire for Medication

Instructions: Please take some time to think about your level of satisfaction or dissatisfaction with the medication (tirbanibulin/Klisyri®) you {‘took at the beginning of’, or ‘most recently took in’} this clinical study. We are interested in your evaluation of the effectiveness and convenience of the medication *since you last used it*. For each question, please select the response that most closely corresponds to your own experiences.

1. How satisfied or dissatisfied are you with the ability of the medication to prevent or treat your condition?

- ₁ Extremely Dissatisfied
- ₂ Very Dissatisfied
- ₃ Dissatisfied
- ₄ Somewhat Satisfied
- ₅ Satisfied
- ₆ Very Satisfied
- ₇ Extremely Satisfied

2. How satisfied or dissatisfied are you with the way the medication relieves your symptoms?

- ₁ Extremely Dissatisfied
- ₂ Very Dissatisfied
- ₃ Dissatisfied
- ₄ Somewhat Satisfied
- ₅ Satisfied
- ₆ Very Satisfied
- ₇ Extremely Satisfied

3. How satisfied or dissatisfied are you with the amount of time it takes the medication to start working?

- ₁ Extremely Dissatisfied
- ₂ Very Dissatisfied
- ₃ Dissatisfied
- ₄ Somewhat Satisfied
- ₅ Satisfied
- ₆ Very Satisfied
- ₇ Extremely Satisfied

4. How easy or difficult is it to use the medication in its current form?

- ₁ Extremely Difficult
- ₂ Very Difficult
- ₃ Difficult
- ₄ Somewhat Easy
- ₅ Easy
- ₆ Very Easy
- ₇ Extremely Easy

5. How easy or difficult is it to plan when you will use the medication each time?

- ₁ Extremely Difficult
- ₂ Very Difficult
- ₃ Difficult
- ₄ Somewhat Easy
- ₅ Easy
- ₆ Very Easy
- ₇ Extremely Easy

6. How convenient or inconvenient is it to take the medication as instructed?

- ₁ Extremely Inconvenient
- ₂ Very Inconvenient
- ₃ Inconvenient
- ₄ Somewhat Convenient
- ₅ Convenient
- ₆ Very Convenient
- ₇ Extremely Convenient

7. Overall, how confident are you that taking this medication is a good thing for you?

- ₁ Not at All Confident
- ₂ A Little Confident
- ₃ Somewhat Confident
- ₄ Very Confident
- ₅ Extremely Confident

8. How certain are you that the good things about your medication outweigh the bad things?

- ₁ Not at All Certain
- ₂ A Little Certain
- ₃ Somewhat Certain
- ₄ Very Certain
- ₅ Extremely Certain

9. Taking all things into account, how satisfied or dissatisfied are you with this medication?

- ₁ Extremely Dissatisfied
- ₂ Very Dissatisfied
- ₃ Dissatisfied
- ₄ Somewhat Satisfied
- ₅ Satisfied
- ₆ Very Satisfied
- ₇ Extremely Satisfied

*Copyright © 2007 Quintiles. All Rights Reserved.

Note:

- Study clinician will be asked to answer ad hoc version of these satisfaction questions, referring to their experience / observation of tirbanibulin effects among their patients.

Skindex-16

THESE QUESTIONS CONCERN THE SKIN CONDITION WHICH HAS BOthered YOU THE MOST DURING THE PAST WEEK

During the past week, how often have you been bothered by:

[figure not shown]
	Never Bothered ↓	•	Always Bothered ↓
1. Your skin condition itching	 0  1  2  3  4  5  6	.	
2. Your skin condition burning or stinging	 0  1  2  3  4  5  6	.	
3. Your skin condition hurting	 0  1  2  3  4  5  6	.	
4. Your skin condition being irritated	 0  1  2  3  4  5  6	.	
5. The persistence / reoccurrence of your skin condition .	 0  1  2  3  4  5  6	.	
6. Worry about your skin condition (For example: that it will spread, get worse, scar, be unpredictable, etc).	 0  1  2  3  4  5  6	.	
7. The appearance of your skin condition	 0  1  2  3  4  5  6	.	
8. Frustration about your skin condition	 0  1  2  3  4  5  6	.	
9. Embarrassment about your skin condition	 0  1  2  3  4  5  6	.	
10. Being annoyed about your skin condition	 0  1  2  3  4  5  6	.	
11. Feeling depressed about your skin condition	 0  1  2  3  4  5  6	.	
12. The effects of your skin condition on your interactions with others (For example: interactions with family, friends, close relationships, etc)	 0  1  2  3  4  5  6	.	
13. The effects of your skin condition on your desire to be with people	 0  1  2  3  4  5  6	.	
14. Your skin condition making it hard to show affection .	 0  1  2  3  4  5  6	.	
15. The effects of your skin condition on your daily activities	 0  1  2  3  4  5  6	.	
16. Your skin condition making it hard to work or do what you enjoy	 0  1  2  3  4  5  6	.	

Have you answered every item? Yes No

Skindex-16 © The Regents of the University of California, 2001

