3.2 Key Study End Points

The primary endpoint of the study will be the PROs, in terms of self-perceived AK symptoms and impact of AK on emotional well-being and functioning as measured using Skindex-16, at Week 8.

The secondary endpoint will be the proportion of Subjects with IGA success, defined as an IGA score of completely cleared (0) or partially cleared (1) in AK status in the treated area at Week 8.

Additional endpoints of the study will include (not exclusively):

- At Week 8, Mean satisfaction scores on TSQM-9 (effectiveness, convenience and overall satisfaction) as well as ad hoc satisfaction questions.
- At Week 8, Mean satisfaction scores on ad hoc physician satisfaction questionnaire.
- At Week 8, proportion of Subjects and Investigators rating the overall appearance of the AK treated area as ‘somewhat improved or much improved.’
- At Week 8, proportion of Subjects and Investigators reporting ‘somewhat likely or very likely’ to consider tirbanibulin in the future to retreat their AK.
- Frequency of documented adverse events (AEs), serious adverse events (SAEs) and LSRs during the first 8-weeks of the study observation period.
- Investigator rating of severity of skin photodamage at Weeks 8 and 24.
- Among Subjects with prior topical treatment experience at baseline:
 - At Week 8, proportion of Subjects and Investigators respectively rating ‘convenience/ease of use’ of tirbanibulin, and ‘overall satisfaction’ with tirbanibulin as ‘somewhat better or much better’ in comparison to previous topical treatments to treat their AK.
 - At Week 8, proportion of Subjects and Investigators respectively rating ‘duration of skin reactions’, ‘severity of skin reactions’ and ‘impact on daily activities due to skin reactions’ related to tirbanibulin, as ‘somewhat better or much better’ in comparison to previous topical treatments to treat their AK.

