6.2 Subject Exclusion Criteria

An individual who meets any of the following criteria will be excluded from participation in this study:

- Patients with any dermatological condition of the face or scalp that could interfere with the clinical evaluations.
- Hypertrophic AK lesions, open wounds or suspected skin cancers within close proximity of the treatment area.
- Anticipated need for in-patient hospitalization or in-patient surgery within the next 2 months.
- Patients unable to comply with the requirements of the study or patients who in the opinion of the study physician should not participate in the study.
- Patients for whom medical chart is inaccessible to physicians to complete baseline data collection.

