7.1 First Study Encounter / Baseline

Baseline data collection will take place at the time of subject enrollment into the study or within a few days of recruitment. The subject encounters are expected to take place during in-person subject visits to the clinic. The recruited Site Investigators and study Subjects will be sent a weblink to the eDCFs and survey respectively for their completion. Subjects will be able to access the surveys on their mobile phone, using a study-specific Mobile App.

The following data elements will be collected at baseline, from patient medical charts and/or per Site Investigator's best clinical judgement based on their recent encounter with the study subject while prescribing tirbanibulin as part of usual care and based on subject's recent past medical history:

- Demographics (e.g., age, gender).
- General clinical characteristics, as documented in medical charts (incl. blood pressure, waist circumference, height/weight measurements, comorbidities).
- AK disease characteristics (incl. AK history, IGA of severity of current skin photodamage in the AK treated area on the face or scalp (using EPQ item)).
- Past AK treatment history (used ever, and those used within the past 6 months).
- Tirbanibulin treatment characteristics (dose, frequency, date of recommendation).
- Concomitant medications (for AK and comorbidities).

The following data elements will be collected at baseline, from study Subjects, via online survey portal or a mobile app:

- Demographics (e.g., gender, race/ethnicity, education, employment/school status, living status).
- Perceptions of AK-related symptoms and impact of AK on Subject QoL, incl. emotional well-being and functioning, using Skindex-16.

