8.1 HRQoL Assessments

The Skindex 16 consists of 16 items that are classified into three domains: symptoms (four items), emotions, (seven items) and functioning (five items) (Chren 2012; Chren et al, 2001). The following questions (items) correspond to each subscale:

Scale	Items
Symptoms	1-4
Emotions	5-11
Functioning	12-16

All items are scored on a seven-point adjectival response scale, with a potential score of 0 to 6. A total score is the average of all 16 items and transformed to a liner scale of 100 varying from 0 (never bothered) to 100 (always bothered). A domain score is determined by the average of scores in each scale within the domain. The higher the score, the more severe is the impairment. The questionnaire will be administered in entirety, at baseline and at Week 8 post-index date.

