12.4 Primary Endpoint Analysis

The primary endpoint of PROs measured using Skindex-16 at Week 8 will be assessed descriptively using the FAS dataset.

The individual item and domain/subscale scores of Skindex-16 will be created per instrument developer instructions, analyzed descriptively (ie, using mean, SD, median, minimum and maximum), for the baseline and Week 8 encounters, treating the responses as categorical variables and/or continuous variable, as appropriate. CFB in Skindex-16 score will be explored and reported using descriptive statistics. For the overall questionnaire data evaluation, no missing data imputation will be applied to compute domain/subscale scores.

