Table 1.4 Patient Self-Assessment: Baseline Skin Texture

Skin Texture *	Baseline (N=x)
S13 If you run your hand across your face and/or scalp, how would you describe the texture:	
S13r1 Dry	n (%)
S13r2 Smooth	n (%)
S13r3 Rough	n (%)
S13r4 Bumpy	n (%)
S13r5 Scaly	n (%)
S13r6 Blistering	n (%)
S13r7 Peeling	n (%)

Note: *Mutually exclusive Data from Patient DCF; X patients had missing data; The denominator for the percentage is the number of patients with available data (N=XX)

Table 1.5 Patient Reported Medication Compliance

Character	Week 8 (N=X)
MC1: Did you take all five doses as prescribed?	
Yes	n (%)
No	n (%)
MC2: If no, how many doses did you miss (out of five total)?	
None [^]	n (%)
One	n (%)
Two	n (%)
Three	n (%)
Four	n (%)
Five	n (%)

Note: Data from Patient DCF. [^]None corresponds to MC1=Yes; all other responses corresponds to MC1>No.

Table 1.6 SKINDEX-16: Patient Response Summary

Domain	Baseline (N=X)	Week 8 (N=X)
Symptoms		
SK1: Over the past week, how often have you been bothered by itching?	n Mean (SD), Median,Min,Max	n Mean (SD), Median,Min,Max
Never Bothered (0)	n (%)	n (%)
(1)	n (%)	n (%)
(2)	n (%)	n (%)
(3)	n (%)	n (%)
(4)	n (%)	n (%)
(5)	n (%)	n (%)
Always Bothered (6)	n (%)	n (%)
Symptoms		
SK2: Over the past week, how often have you been bothered by Burning or Stinging?	n Mean (SD), Median,Min,Max	n Mean (SD), Median,Min,Max
Never Bothered (0)	n (%)	n (%)
(1)	n (%)	n (%)
(2)	n (%)	n (%)
(3)	n (%)	n (%)
(4)	n (%)	n (%)
(5)	n (%)	n (%)
Always Bothered (6)	n (%)	n (%)
Symptoms		
SK3: Over the past week, how often have you been bothered by your skin condition hurting?	n Mean (SD), Median,Min,Max	n Mean (SD), Median,Min,Max
Never Bothered(0)	n (%)	n (%)
(1)	n (%)	n (%)
(2)	n (%)	n (%)
(3)	n (%)	n (%)

(4)	n (%)	n (%)
(5)	n (%)	n (%)
Always Bothered (6)	n (%)	n (%)
Symptoms		
SK4: Over the past week, how often have you been bothered by your skin condition being irritated?	n Mean (SD), Median,Min,Max	n Mean (SD), Median,Min,Max
Never Bothered(0)	n (%)	n (%)
(1)	n (%)	n (%)
(2)	n (%)	n (%)
(3)	n (%)	n (%)
(4)	n (%)	n (%)
(5)	n (%)	n (%)
Always Bothered (6)	n (%)	n (%)
Emotions		
SK5: Over the past week, how often have you been bothered by persistence/recurrence of skin condition?	n Mean (SD), Median,Min,Max	n Mean (SD), Median,Min,Max
Never Bothered(0)	n (%)	n (%)
(1)	n (%)	n (%)
(2)	n (%)	n (%)
(3)	n (%)	n (%)
(4)	n (%)	n (%)
(5)	n (%)	n (%)
Always Bothered (6)	n (%)	n (%)
Emotions		

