Private health insurance	n (%)	
Medicaid	n (%)	
Medicare	n (%)	
Uninsured	n (%)	
Other: Self Pay	n (%)	
Not available	n (%)	
PC3 Height (in inches)	N, Mean (SD), Median, Min, Max	
PC4 Weight (in lbs/pound)	N, Mean (SD), Median, Min, Max	
PC5 Waist circumference (in inches)	N, Mean (SD), Median, Min, Max	
Body Mass Index (BMI - calculated)	N, Mean (SD), Median, Min, Max	
PC6 Blood pressure (in mm HG)		
Systolic	N, Mean (SD), Median, Min, Max	
Diastolic	N, Mean (SD), Median, Min, Max	
PC7 Concomitant (comorbid) conditions		
None	n (%)	
Anxiety	n (%)	
Anemia or other blood disease	n (%)	
Asthma	n (%)	
Atopic dermatitis	n (%)	
Cancer (of any type)	n (%)	
Crohn's disease / IBD	n (%)	
Diabetes	n (%)	
Depression	n (%)	
Dyslipidemia/Hyperlipidemia	n (%)	
Gastroesophageal reflux disease	n (%)	
Heart disease	n (%)	
Hypertension	n (%)	
Kidney disease	n (%)	

Liver damage or disease	n (%)
Lung disease	n (%)
Osteoarthritis, degenerative arthritis	n (%)
Other gastrointestinal disease	n (%)
Other	n (%)
X Y Z	n (%)

PC8 History of Skin Cancer

Yes	n (%)
No	n (%)

AK2 Fitzpatrick Skin-type classification?

Type I	n (%)
Type II	n (%)
Type III	n (%)
Type IV	n (%)
Type V	n (%)
Type VI	n (%)

Note: Data from Clinician DCF; X patients had missing data; The denominator for the percentage is the number of patients with available data (N=X)

Table 2.4 Tirbanibulin Treatment Characteristics for the Original Treated Area

Character	Baseline (N=x)
TH1B: Prescription dose 1. 1% tirbanibulin, single-dose packets 2. Other, please specify [TH1Br2oe] a. X	n (%)
TH1C: Prescription frequency 1. Once daily for 5 consecutive days 2. Other, please specify: [TH1Cr2oe] a. X	n (%)

Table 2.5 Area of Tirbanibulin Treatment for the Original Treated Area

Character	Baseline (N=x)
AK3A1: What is the AK treatment area you have identified for the patient, to apply tirbanibulin (Klisyri®)?	
Left	
Face	n (%)
Scalp	n (%)
Right	
Face	n (%)
Scalp	n (%)
Center	
Face	n (%)
Scalp	n (%)
Unknown	
Face	n (%)
Scalp	n (%)
Overall	
Face (any area)	n (%)
Scalp (any area)	n (%)

Table 2.6 Tirbanibulin Treatment Completion Rate for the Original Treated Area

Character	Week 8 (N=X)
P2: Did the patient complete 5-day treatment course of tirbanibulin (Klisyri®) at the beginning of the study? (N=X)	
Yes	n (%)
No	n (%)

Note: Data from clinician CRF.

Table 2.7 Clinician Evaluation of Current Severity of Photodamage in the Original Treated Area

Character	Baseline (N=X)	Week 8 (N=x)	Week 24 (N=X)

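### The primary endpoint is defined as AK symptoms and impact, but Skindex-16 as printed asks about the most bothersome skin condition, and the plan does not record which condition was rated

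*Protocol*

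**What the plan says.** Protocol 3.2 and SAP 2.2 define the primary endpoint as "self-perceived AK symptoms and impact of AK on emotional well-being and functioning as measured using Skindex-16, at Week 8". Protocol 7.1 describes the baseline patient survey in the same terms: "Perceptions of AK-related symptoms and impact of AK on Subject QoL, incl. emotional well-being and functioning, using Skindex-16". Protocol 7.3 does so for Week 8.

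The instrument, reproduced in Appendix B of the protocol and again in the SAP, opens with "THESE QUESTIONS CONCERN THE SKIN CONDITION WHICH HAS BOthered YOU THE MOST DURING THE PAST WEEK". Its items then speak of the patient's skin condition without naming one. The item wording in SAP Table 1.6 adds no anchor, for example "SK1: Over the past week, how often have you been bothered by itching".

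On timing, Protocol 8.1 states: "The questionnaire will be administered in entirety, at baseline and at Week 8 post-index date". On analysis, Protocol 12.4 and SAP 6.4 state: "CFB in Skindex-16 score will be explored and reported using descriptive statistics". SAP Tables 1.7 to 1.9 attach p-values to that change.

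The eligibility rule closest to the point excludes "Patients with any dermatological condition of the face or scalp that could interfere with the clinical evaluations" (Protocol 6.2, SAP 3.2).

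**The concern.** The endpoint names a disease, whereas the form names whatever bothered the patient most in the preceding week and makes that selection afresh at each visit. A change from baseline can be read as a change in AK only if the patient had AK in mind both times, and the plan neither secures this nor observes it.

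Two patients show what is at stake. One has AK that improves but rates another skin problem at Week 8, and the AK improvement is lost from the score. Another rates a flare of something else at baseline, it settles, and the study records an improvement on tirbanibulin. The study has a single arm, so no control group offsets such shifts. More patients would not reduce them. Because the rated condition is not recorded, no later analysis can identify who was affected.

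**Working it through.** There is no stated figure to reproduce: Protocol 12.1 gives about 300 subjects on feasibility grounds, with no assumed effect or standard deviation. The check is mainly textual, followed by an illustration.

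**Textual check**

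- Target: AK symptoms and impact (Protocol 3.2, 7.1, 7.3; SAP 2.2).
- What the patient is asked to rate: the most bothersome skin condition of the past week (Appendix B, both documents).
- Instruction to answer for AK: none found in either document.
- Record of the condition rated, or a check that it is the same at both visits: none found.
- Eligibility: only interfering conditions of the face or scalp are excluded. Skin disease elsewhere on the body, or arising after enrollment, is not covered.
- Other instruments in the same appendix: the Expert Panel Questionnaire items on appearance, looks, texture and skin reactions name the AK treated area, and TSQM-9 names tirbanibulin. The primary instrument is the one left without an anchor.
- AK-specific alternative: Protocol 2.1 describes AKQoL and 2.2 cites it in the rationale, but no encounter schedules it.

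**Illustration (all inputs assumed)**

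Let d be the true mean change in AK on the 0 to 100 scale, q the share of patients who rate something other than AK at one or both visits, and c the mean change those patients show.

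Observed mean change = (1 − q)·d + q·c, so the distortion is q·(c − d).

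Case A: the same non-AK condition is rated at both visits and does not change, so c = 0.
Case B: AK is rated at baseline with score 25, and another condition at Week 8 with score 10 or 30, so c = 10 − 25 = −15 or c = 30 − 25 = +5.

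| d | q | Case A | Case B, score 10 | Case B, score 30 |
|---|---|---|---|---|
| −10 | 5% | −9.5 | −10.25 | −9.25 |
| −10 | 30% | −7.0 | −11.5 | −5.5 |
| −20 | 5% | −19.0 | −19.75 | −18.75 |
| −20 | 30% | −14.0 | −18.5 | −12.5 |

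For example, with d = −10 and q = 30%: 0.70 × (−10) + 0.30 × 5 = −5.5, and 0.70 × (−10) + 0.30 × (−15) = −11.5.

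For scale, the 95% half-width of a mean change at N = 300 is 1.96 × SD / √300, which is 1.7, 2.3 or 2.8 points for an assumed SD of 15, 20 or 25. The shifts in the table run from 0.25 points (−10 read as −10.25) to 7.5 points (−20 read as −12.5), so they can be negligible or can exceed sampling error. In one column a true −10 is exaggerated, so the direction is not fixed either.

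**The case against.** The strongest reply is that this is mostly a matter of labelling. Protocol 3.1 states the primary objective as health-related quality of life among subjects with AK, and a skin-related score in AK patients answers that. Protocol 2.1 presents Skindex-16 as validated and reports that an expert panel chose it, and the header appears on a copyrighted form that the study has reason to leave unaltered. Patients consent to an AK study, use a study app, and are asked in the same survey what led them to seek AK treatment. Many will answer for AK anyway, especially at baseline. The app screens are not shown, so an AK instruction there cannot be ruled out, although neither document mentions one.

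Most of this stands, and it limits the point. It does not remove the conflict between Protocol 3.2 and the form, because the endpoint and the visit descriptions claim AK specifically.

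Stronger readings that a reader might infer also fail on the documents:

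- That once treated AK clears, the Week 8 answers must concern something else. A cleared patient with no other complaint can answer zero, which is a valid AK result. Items on recurrence and worry can still apply to AK after lesions clear, and IGA success includes partial clearance.
- That AK outside the treated area is off target. Only the secondary endpoint is confined to the treated area.
- That the "Atopic dermatitis" line in SAP Table 2.3 shows other skin disease to be expected. It is one entry in a general comorbidity list and says nothing about prevalence.

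**Conclusion.** The point holds as a mismatch between what the primary endpoint claims and what the printed instrument asks, with no means in the plan of seeing how much it matters. For some patients the two scores may refer to different conditions or to a condition other than AK.

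No size can be attached. A reader might take assumed shares of 10% to 30% and assumed score gaps of 20 to 40 points, multiply them (0.10 × 20 = 2; 0.30 × 40 = 12) and conclude that improvement is understated by 2 to 12 points. The documents do not support that: they give neither input, the product counts Week 8 only although the same selection operates at baseline, and the direction is uncertain. Nor do they support saying that the primary objective goes unanswered. What is affected is whether the reported change may be called a change in AK symptoms and impact. The conclusion assumes that the form is administered as printed.

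**What to change.** Leave the 16 items unchanged. After Skindex-16, at baseline and at Week 8, add one question: *Which skin condition did you have in mind: AK on the face or scalp area treated or to be treated; AK elsewhere; another skin condition; none bothered me?*

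In SAP 6.4 and Table 1.8:

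- Tabulate the answers at each visit.
- Repeat the three domain scores and their change from baseline as a sensitivity display for subjects whose baseline reference was AK at any site, keeping all of them whatever they answer at Week 8.
- Report a change of reference at Week 8 descriptively only. Splitting the results by it would condition on outcome, since patients whose AK clears may be the ones more likely to name something else.

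The display does not recover an AK score for patients who changed reference, but the tabulation shows how many there are.

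The cost is one app item at two existing encounters, a short amendment, one extra block in Table 1.8, and a smaller n in the sensitivity display.

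The SAP puts the safety population at 300 and words its exclusion criteria partly in the past tense, so baseline collection may be complete. If the data are already collected, restate the endpoint in Protocol 3.2 and SAP 2.2 as skin-related quality of life for the most bothersome skin condition among patients with AK, and do not report the change from baseline as a change in AK symptoms and impact. That needs no new data.
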